1. ABSTRACT

Interstitial cystitis/bladder pain syndrome (IC/BPS) is a debilitating, incurable, and costly pain condition affecting approximately 3-8 million individuals in the United States and is extremely challenging to treat. Evidence suggests psychosocial factors accompany and intensify the illness.

Unaddressed psychosocial co-morbidities are associated with reduced functionality and poorer outcomes, which suggests that psychosocial symptoms and bladder-specific symptoms reinforce each other. While psychosocial self-management interventions have demonstrated efficacy for other pain conditions, the IC/BPS field lacks the gold standard – randomized controlled trials – studying these interventions. At the same time, the chronic pain field is adopting a new approach driven by mechanisms of illness and treatment. Growing evidence suggests that subgroups (called “phenotypes”) of patients with IC/BPS respond differently to medical intervention. Presence of central sensitization (CS) largely defines patient subgroups and may be a biological factor affecting response to medical treatment. The **overall goal** of this project is to fully develop, optimize, and evaluate a patient-centered CBT self-management intervention specific to IC/BPS. To achieve this goal, we will develop (Aim 1) and test (Aim 2) an empirically-based psychosocial treatment for IC/BPS compared to attention control, while examining pain mechanisms and subgroup characteristics that may alter treatment response (Aim 3). We **hypothesize** that a) inclusion of a self-management intervention will be more effective than a control treatment for IC/BPS, and that b) treatment effects will be moderated by degree of psychological co-morbidity, presence of chronic overlapping pain conditions, and elevated central sensitization. Successful completion of these aims will determine whether the addition of a tailored self-management intervention for IC/BPS will improve outcomes compared to control, whether particular subgroups are more responsive to this intervention, and whether a biological mechanism (CS) influences treatment responsiveness.

2. BACKGROUND

Interstitial cystitis/bladder pain syndrome (IC/BPS) is a debilitating, incurable, and costly pain condition affecting approximately 3-8 million individuals in the United States.¹ Pain is the hallmark symptom of IC/BPS – which occurs in the pelvis, urogenital floor, or external genitalia.² Patients also experience urinary urgency, pressure/discomfort, and/or urinary frequency.³ The economic burden of the condition is substantial, costing the healthcare system upwards of \$750 million a year.² Understanding of IC/BPS pathophysiology is limited, and most treatments target symptom control. Between 1992-2001, rates of physician office visits for IC/BPS tripled and hospital outpatient visits doubled². Current biomedically-based treatments lack effectiveness.⁴

A high-need, high-cost population,⁵ IC/BPS patients have medically complex presentations and often do not respond to surgical intervention. Psychosocial co-morbidities such as anxiety, depression, quality of life, and trauma-related symptoms accompany and intensify the illness.^{6,7,8} Table 1 represents a sample of

chronic pain patients with and without IC/BPS (as defined by epidemiological criteria) collected in a recent study at VUMC (████████). Per Table 1, compared to chronic pain conditions without IC/BPS, those with IC/BPS symptoms have significantly worsened psychological functioning, impaired coping, multi-symptomatic complaints, and increased perceived pain.

Table 1: Comparison of psychosocial and pain experiencing in chronic pain (N=137) vs. IC/BPS (N=63) patients using a Wilcoxon Test reported as median (SD)

Assessment Domain	Chronic Pain (N=137) p	IC/BPS (N=63)	
Pain Experiencing (MPQ-II)	3.0 (1.6)	3.6 (2.0)	0.041*
Central Sensitization (CSI-A)	42.0 (16)	57.0 (17)	<0.001***
Catastrophizing (PCS)	16.1 (10.6)	22.8 (13.0)	0.007**
Anxiety Sensitivity (ASI)	15.0 (12)	23.0 (17.0)	0.003**
Anxiety (HADS-A)	8.5 (4.4)	11.0 (5.0)	0.001***
Depression (HADS-D)	6.4 (4.2)	8.2 (4.8)	0.012*
Childhood Trauma Exposure	40.0 (29)	46.0 (28)	0.062
Adulthood Trauma Exposure	5.8 (4.0)	5.5 (3.8)	0.63
PTSD Assessment (PCL-5)	20.1 (15.4)	28.9 (20.9)	0.009**

Psychosocial factors precipitate and perpetuate IC/BPS symptoms, and there is a documented genetic linkage of IC/BPS with panic disorder.⁹ Animal studies show that exposure to psychological stress augments bladder nociception,¹⁰ and a large epidemiological study reported that those with IC/BPS and uncontrolled depression or anxiety work less and experience significantly greater impairment and urinary symptoms.¹¹ In chronic pain, unaddressed psychosocial factors can shape patient perceptions and behavior and lead to poorer, functioning, prognosis, and response to treatment.¹²⁻¹⁵ This suggests both a strong association between and reinforcement of psychosocial symptoms and bladder-specific symptoms.

Overall, IC/BPS is a biopsychosocial condition prompting both medical and psychosocial interventions to achieve optimal outcomes.

A Mechanistic Approach to Treatment

IC/BPS falls into a class of conditions recently termed by the U.S. Congress and National Institute of Health as Chronic Overlapping Pain Conditions (COPC).¹⁶ These conditions often co-occur, affect women predominantly, and are bound by a unifying pathophysiological mechanism of pain or sensory amplification (central sensitivity¹⁷). In addition to IC/BPS, other COPC examples include fibromyalgia and irritable bowel syndrome. **Researchers are moving away from a disease-specific to a mechanistic classification of chronic pain.** Current research designed to show treatment efficacy in mechanism-based subtypes will inform and help tailor future treatment regimens based upon a patient's mechanistic presentation.¹⁸

Within each COPC diagnostic category, subgroups of patients, or “phenotypes”, emerge that are largely defined by symptom severity, sensory sensitivity, and psychosocial factors that identify those more susceptible to chronic pain and its effects.¹⁸ Leading researchers¹⁹ have defined three IC/BPS phenotypes based on chronic pain distribution: 1) localized pelvic pain 2) pain in 1-2 regions outside the pelvis and 3) widespread pain.²⁰ In total, 75% of women with IC/BPS report pain outside of the pelvis. Those with widespread pain (38%) have worsened pain severity, psychological distress, and sleep disturbance.²⁰ It is theorized that individuals with widespread pain, or higher degrees of central sensitivity, respond less to biomedical treatments and may benefit more from an integrative treatment plan including cognitive-behavioral or self-management interventions to comprehensively address pain interference, sleep disturbance, and mood.

National guidelines recommend psychosocial interventions as a first-line treatment for IC/BPS.²¹ But these interventions are underutilized secondary to limitations in provider availability and time constraints. We do not know if the recommended “stress management” therapies suggested in these guidelines sufficiently meet patient needs or if patients require a broader pain self-management approach like those used in other forms of chronic pain.²² Recommended psychological interventions include cognitive-behavioral self-management programs, which help patients build confidence and skills in preventing, coping and reducing pain.²³ There is a paucity of randomized controlled trials evaluating how and in whom these interventions work. Little is known about the impact of treating psychosocial factors on illness presentation, or how patients of different disease phenotypes respond to this type of treatment. Such knowledge may permit targeting of scarce psychosocial treatment resources towards those most likely to benefit from them.

Psychosocial self-management interventions could benefit patients by: 1) bolstering self-efficacy and increasing social support – known to buffer the impact of symptoms,^{24,25} 2) improving medical treatment adherence,²⁶ and 3) reducing the impact of psychological distress that may intensify symptoms. Self-management may be preferable as patients are often not responsive to psychotropic medications.²⁷ In our IC/BPS urology clinic at VUMC, of *8 patients treated with self-management (N = 8), 6 of 8 (75%) patients reported significantly and meaningfully improved urinary symptoms (X = 4.85) post-treatment*, as measured by the American Urological Association Symptom Index (AUASI²⁸) – where a 3 point change in symptoms is considered clinically meaningful.²⁹ Further, the two patients with unchanged urinary symptoms reported clinically meaningful reductions in pain intensity on the Numeric Rating Scale-11.³⁰ **While pain and urologic outcomes need to be analyzed separately,³¹ they should be considered in unison.**

Psychological distress occurs regardless of severity of pain and urinary symptoms.^{32,33} Many patients with only moderate symptoms have significant psychological burden.^{32,34} Thus, patients at all stages of this illness may benefit from self-management. A recent survey by the Interstitial Cystitis Association (N

= 1,982³⁵) revealed significant interest in employing self-management strategies such as stress reduction, behavioral sleep strategies, relaxation, and active coping strategies to alleviate symptoms. These findings and our preliminary data show that patients are open to and interested in this line of intervention.

Despite demonstrated efficacy in other pain conditions,^{36,22} and patient openness to intervention, there has yet to be a high-quality randomized control trial evaluating the impact of psychosocial interventions for IC/BPS and no study of how patient subgroups impact treatment response. Evidence from the Multidisciplinary Approach to Pelvic Pain (MAPP) multisite study indicates that subgroups (“phenotypes”) of patients with IC/BPS respond differently to medical intervention.³⁷ Presence of central sensitization, a centrally-mediated facilitation of pain responsiveness, largely defines this patient phenotype^{31,20} and may be a biological factor mediating treatment response.

The 2016 NIDDK Strategic Plan strongly supports research to increase treatment options for IC/BPS. The 2015 National Pain Strategy calls for a stronger focus on patient-centered outcome research for chronic pain conditions, generally including cognitive-behavioral (CBT) self-management strategies. Our preliminary study (n=8) of a tailored self-management intervention for IC/BPS showed that 6 of 8 (75%) patients reported significant and clinically meaningful reduction in urinary symptoms. The **overall goal** of this project is to fully develop, optimize, and evaluate a patient-centered CBT self-management intervention specific to IC/BPS. We **hypothesize** that 1) inclusion of a self-management intervention will be more effective than *[attention control]* for IC/BPS, and that 2) treatment effects will be moderated by degree of psychological co-morbidity, presence of chronic overlapping pain conditions, and elevated central sensitization. Specific aims include:

3. SPECIFIC AIMS

Aim 1: To construct a patient-centered CBT self-management (SM) intervention specific to IC/BPS. We will construct a self-management intervention for IC/BPS with information compiled from patient focus groups (preliminary data), clinical expertise, and effective components of self-management interventions in associated conditions. We will work in collaboration with IC/BPS experts and utilize research collected from an ongoing project (MAPP) to inform intervention design. We will then invite focus group participants to return and review the intervention package for acceptability.

Aim 2: To obtain pilot data comparing the effectiveness of integrating SM interventions into standard care (N = 50) to attention control (AC, N = 25) in improving targeted genitourinary symptoms (GUPI,⁴ primary outcome) and secondary outcomes of pain, distress, and quality of life. We hypothesize that individuals receiving the SM intervention will show improved outcomes relative to control [AC].

Aim 3: To determine whether patient phenotype moderates treatment response to a SM intervention. We will define patient phenotype by: assessment of temporal summation (as a marker of central sensitization), degree of psychological co-morbidities, and presence of chronic overlapping pain conditions. We hypothesize that (1) higher levels of pre-treatment psychological co-morbidities (e.g. depression levels) will be associated with greater SM treatment efficacy, (2) we hypothesize that greater baseline temporal summation will be associated with greater SM treatment efficacy, and (3) we hypothesize that participants with more chronic overlapping pain conditions will exhibit greater SM treatment efficacy.

Successful completion of these aims will determine whether the addition of a tailored self-management intervention for IC/BPS will improve patient symptoms and function, whether particular patient

subgroups are more responsive to this intervention, and whether a potential biological mechanism (central sensitization) influences treatment responsiveness. We summarize these aims in the table below.

	Summary	Hypothesis
Aim 1	To construct a patient-centered CBT self-management (SM) intervention specific to IC/BPS.	N/A
Aim 2	To obtain pilot data comparing the effectiveness of integrating SM interventions into standard care to attention control in improving targeted genitourinary symptoms and secondary outcomes of pain, distress, and quality of life.	We hypothesize that individuals receiving the SM intervention will show improved outcomes relative to control.
Aim 3	To determine whether patient phenotype moderates treatment response to a SM intervention.	Higher levels of pre-treatment psychological co-morbidities (e.g. depression levels) will be associated with greater SM treatment efficacy. Greater baseline temporal summation will be associated with greater SM treatment efficacy. Participants with more chronic overlapping pain conditions will exhibit greater SM treatment efficacy.

4. PARTICIPANT SELECTION

4.1 Recruitment

We will recruit **over a period of three years**. The target population includes the following counties in middle Tennessee that surround the Nashville area: Davidson, Montgomery, Rutherford, and Williamson. According to 2017 U.S. census data, these four counties are home to 1.43 million individuals and are racially, ethnically, socioeconomically, and geographically diverse.

We will recruit internally via VUMC and externally in the surrounding community to meet recruitment goals. We will recruit individuals with IC/BPS from VUMC clinics. Externally, we will recruit individuals through ResearchMatch,⁵ the VUMC Research Listserv, MyResearch (MRAV) database, online, and in area hospitals and clinics – which the PI has successfully used in previous studies. In addition to VUMC, our prospective recruitment sources include patient organizations, community clinics, support group pages, media advertisements, social media, and local university clinics. Further, we will contact eligible individuals from former investigations conducted by the PI (e. [REDACTED]
[REDACTED] and co-mentors [name], [name], and [name] who previously consented for further follow-up and expressed interest in participating in further study.

MyResearch (MRAV) is a participant repository recruitment tool available to Vanderbilt researchers that reaches over 18,000 My Health at Vanderbilt users that have previously confirmed they would like to be contacted directly for research. This repository provides investigators a forum for advertising for volunteers for a specific study. Email notifications are limited to IRB approved language (see attached script for approval), describe study specifics and provide contact information. To utilize this initiative, we will complete a MyResearch Access Request with the approved language that is reviewed to ensure the recruitment tool and requested number of contacts are appropriate.

Reporting Workbench (RWB) Reports is a new recruitment tool available to VUMC researchers available/viewable in eStar. These reports are developed using real-time data and can be customized to meet study-specific inclusion/exclusion criteria. Research team members with eStar access and collaboration with the RWB team, and access to the Report Groups, can view/run the reports as frequently as needed. While a RWB report only displays certain variables, it provides easy access to a patient's record for additional screening and confirmation of eligibility.

The RWB Report requested for this study will be created by filtering on the following variables
– inclusion criteria: 18+, living in KY/TN, ICD N30.10/N30.11, patients seen in the following clinics
- Vanderbilt One Hundred Oaks Primary Care, Vanderbilt Primary Care Franklin, Vanderbilt Center for Women's Health, Vanderbilt Center for Women's Health Cool Springs, Vanderbilt Urology Cool Springs, Vanderbilt Urology TVC3; exclusion criteria: any exclusion criteria in the protocol that may be computable in the EHR. Variables to be displayed in the report will include MRN and demographics, as well as patient research contact preference. Additional chart screening can be performed to confirm eligibility.

This report provides a list of potential study-eligible individuals. A subset of these potentially eligible individuals may have also indicated their preference to be contacted **directly** for research as indicated by OK to Contact or Do Not Contact. If the patient did not explicitly give their permission for OK to Contact, their preference will be listed as Do Not Contact. Patient Research Contact preference will be listed in a column in the RWB report.

We are proposing to use RWB to contact study-eligible individuals in two different ways: one by contact through study eligible individuals' medical providers similar to the process used when using the Subject Locator tool, and second to directly contact those who have previously indicated they would like to be contacted for potential research participation.

1. For those patients with Do Not Contact for their research contact preference, we propose to contact their providers to request that they connect with the patient about this study opportunity, should they deem it appropriate. We will provide them with a recruitment message, once again including access to our REDCap Interest Form, to distribute to patients accordingly. [name] has extensive connections to providers through the IC Clinic and throughout VUMC, many of whom have expressed enthusiastic interest about aiding in recruitment efforts.
2. For those patients with Ok to Contact for their research contact preference, we propose direct-messaging, in eStar or via email, these patients with a recruitment message that includes a link to our IRB-approved Interest Form. In eStar, these patients will be sent our direct recruitment message up to two times. From there they can either reply to our message, contact our study team,

or fill out our REDCap form. Per our recruitment procedures, we will give them a final phone screening if they indicate interest.

This condition is greatly understudied and needs more research, as patients subjectively report that even diagnosis alone can take years of ruling out alternative conditions. We also have excellent rates of study enrollment and retention in our first year. Thus, providers and participants alike have largely been overwhelmingly positive about this study. We believe that our goal of $n = 75$ is in reach and could be helped greatly by incorporation of these EHR-based recruitment options.

One online recruitment tool we will include is researchmatch.org. **ResearchMatch**⁵ is a national electronic, web-based recruitment tool that was created through the Clinical & Translational Science Awards Consortium in 2009 and is maintained at Vanderbilt University as an IRB-approved data repository (see [REDACTED]). Regarding ResearchMatch, we are requesting IRB approval to send the appended study recruitment message to potential study volunteers through ResearchMatch.org. ResearchMatch confirms IRB-approved recruitment language and that direct study contact information has been removed (email/phone) before sending the study announcement through ResearchMatch to volunteers that appear to be a good match for the study. Potential volunteers will be contacted using the IRB-approved content (attached for approval). Volunteers will then have the option of replying yes or no through a set of quick links available in the notification. If a volunteer chose to respond in the affirmative they will authorize ResearchMatch to release their contact information to me and I will be responsible for managing that information according to institutional guidelines.

Accompanying ResearchMatch, we will also access the **Research Notifications Distribution List**, where VUMC researchers can use a listserv to access over 18,000 faculty, staff, and community members who may be interested in research. This tool uses IRB-approved recruitment scripts (see attached script for approval) and distributes advertisements to the Vanderbilt community and members of the general public locally who have 'opted in' to receive these emails. We successfully used these tools to recruit for a recent study on IC/BPS conducting focus groups to collect preliminary data for this proposal ([REDACTED]). We will also be registered on clinicaltrials.gov as a clinical trial and anticipate participant interest from this registration.

We will facilitate recruitment from **existing VUMC clinical services** targeting current patients and new referrals at VUMC entities including urology, the Osher Center for Integrative Medicine, primary care, and rheumatology clinics as examples. This includes patients from the existing IC/BPS clinic in outpatient urology and additional clinics conducted by study co-mentors ([REDACTED])

[REDACTED] In the outpatient IC/BPS clinic at Vanderbilt, we see 2-3 new patients per week, or an average of 10 per month. We will also recruit with assistance from outpatient providers at the Osher Center for Integrative Medicine (OCIM) who evaluate and treat adults with chronic overlapping pain conditions, whom the PI has worked with for 5 years, and include [REDACTED]
[REDACTED]

To specifically target individuals diagnosed with IC/BPS, we will also use VUMC's **Subject Locator** to identify potential research subjects based on data available in VUMC clinical systems (e.g. STAR Panel, EPIC, WizOrder, Clinic Scheduling). The subject locator program is part of a toolset available through

the Vanderbilt Center for Translational Research that enables teams to specify inclusion/exclusion criteria for a specific study. Study criteria are codified for computable use and combined with data coming through VU Clinical Systems to proactively identify individuals who might qualify for a study. Once a 'match' is made, research study personnel are alerted using confidential messaging or a secure web portal and they may then use the information to further review the patient's information using the Vanderbilt Electronic Medical Record. If the patient is further deemed a candidate for the study, the study personnel will notify the patient's care provider who will then ask the patient if they would be interested in communicating with study personnel about research participation, at which point the potential subject will be screened for inclusion and exclusion criteria.

In instances where participants have not previously consented to being contacted for follow-up, or responded to a study announcement expressing interest, individuals initially approaching potential participants about the study will be those with an existing clinical relationship (e.g. providers at OCIM) prior to study screening.

We will monitor enrollment **diversity** on a regular basis throughout the study. Our inclusion of local hospitals and clinics in the community such as Nashville General Hospital at Meharry (a historically African-American academic health science center) and will enhance our ability to achieve our goals for minority representation and gender distribution, as both of these clinical services treat a large number of minority patients and men. The PI's primary mentor (████████) is an attending at Nashville General Hospital and has successfully recruited for clinical trials at this site, and will assist the candidate with facilitating recruitment as needed to meet recruitment goals.

Recruitment tracking will occur through our study databases. We will have a REDcap study database for screening, as well as a spreadsheet for tracking recruitment, enrollment, and scheduling, to assure we appropriately capture all subjects screened. This will also allow us to maintain records of criteria leading to study exclusion, and once subjects have enrolled, will capture reasons for study discontinuation or early withdrawal. This will assure we capture all required information for accurate completion of the CONSORT checklist and flow diagram.

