4.4 Exclusion criteria

1. Comorbid neurological conditions including spinal cord injury or systematic neurologic illnesses, or central nervous system diseases such as brain tumor or stroke.
2. Current or history of diagnosis of primary psychotic or major thought disorder within the past five years;
3. Hospitalization for psychiatric reasons other than suicidal ideation, homicidal ideation, and/or PTSD (within the past 5 years);
4. Psychiatric or behavioral conditions in which symptoms are unstable or severe (e.g. current delirium, mania, psychosis, active suicidal ideation, homicidal ideation, substance abuse dependency) reported within the past six months;
5. Non-English speaking
6. Presenting symptoms at time of screening that would interfere with participation, specifically active suicidal ideation with intent to harm oneself or active delusional or psychotic thinking;

7. Difficulties or limitations communicating over the telephone.
8. Any planned life events that would interfere with participating in the key elements of the study.
9. Any major active medical issues that could preclude participation.
10. Currently being treated for cancer.
11. Cancer-related pain.
12. Currently engaged in individual counseling/psychotherapy or unwilling to pause this treatment for the trial duration.

*There will not be an upper age cutoff for study participation because individuals of all ages can be successfully treated, including those over 80 years old.

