9. STATISTICAL CONSIDERATIONS

9.1 Analytic Plan by Aim

Aim 1: To construct a patient-centered CBT self-management (SM) intervention specific to IC/BPS. Pre-work for this aim will include a theme analysis of coded transcripts from focus groups using NVivo 9 to code, analyze, and interpret transcripts using elements of grounded theory.⁷⁸ For the project period, this aim will primarily involve consolidating qualitative work and will use descriptive statistics where appropriate.

Aim 2: To obtain preliminary data comparing the effectiveness of integrating SM interventions into usual treatment (N = 50) to control (AC, N = 25) in improving targeted primary (symptom improvement [≥ 7 point reduction in GUPI]) and secondary (pain, distress, quality of life) outcomes.

Power and sample size considerations: ■ are comparing GUPI-Total Score, a continuous variable, between the SM group and a matched AC group with a 2:1 randomization scheme. The GUPI-Total Score tends to be normally distributed with a standard deviation of 8.61.^{47,79} A 7-point decrease in total GUPI score is considered clinically meaningful⁷⁹ and a robust assessment of response to treatment.⁴

Assuming a Type I error of 0.05 and power of .90, we will need 50 experimental subjects and 25 control subjects to reject the null hypothesis that the sample means of both treatment groups are equal post-treatment. ■ intend to have 50 experimental and 25 control subjects to obtain even groups for analytical purposes, as recommended by ■ DSBM. Given our use of statistical models, ■ power is increased when ■ appropriately adjust for covariates.

■ will test the hypothesis that those receiving the SM intervention will show improved outcomes relative to AC. ■ will use generalized linear mixed models to compare responses on the Genitourinary Pain Index (GUPI⁸⁰-Primary Outcome) between treatment groups, adjusting for baseline GUPI and covariates. As recent evidence recommends the examination of pain and urinary symptoms separately,²⁵ ■ will examine the GUPI pain subscale and GUPI urinary subscale separately in secondary analyses. ■ will perform one interim analysis at approximately 50% completion of data collection using the O'Brien-Fleming method to preserve alpha accounting for repeat testing.

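### Eligibility screening does not ask about earlier receipt of the IC/BPS self-management intervention or review of its package, although recruitment draws on the clinic, studies and tools where that exposure arose

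*Combined protocol and SAP*

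**What the plan says.** **Who may have been exposed.** Section 2 (Background) describes eight patients treated with self-management in the centre's own IC/BPS urology clinic, and later says: "Our preliminary study (n=8) of a tailored self-management intervention for IC/BPS showed that 6 of 8 (75%) patients reported significant" reductions in urinary symptoms. Separately, section 3 (Aim 1) says of the new package: "We will then invite focus group participants to return and review the intervention package for acceptability". The number of focus-group participants is not given.

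**Where the trial recruits.** Section 4.1 lists, among many sources:

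- The same clinic: "This includes patients from the existing IC/BPS clinic in outpatient urology".
- Earlier studies: "we will contact eligible individuals from former investigations conducted by the PI". This is limited to people who agreed to follow-up contact and showed interest; the named examples are redacted.
- ResearchMatch and the research listserv, which section 4.1 says were also used to recruit the focus groups.

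**What is screened.** The nearest criterion is item 12 of section 4.4: "Currently engaged in individual counseling/psychotherapy or unwilling to pause this treatment for the trial duration". It concerns therapy in progress. The inclusion criteria (4.3), the other exclusions (4.4), the referral form (Appendix A), the telephone and in-person scripts (Appendices B and C) and the checklist (Appendix D) contain nothing on past receipt of the intervention or past review of its materials. Section 9.1 has no covariate, stratum or sensitivity analysis for prior exposure.

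**The concern.** Aim 2 estimates what SM adds over AC. Self-management teaches skills that may persist. A patient who already has them may improve less when given SM, so the SM-AC difference among such patients may be smaller than among untreated ones. Mixing the two groups would pull the average difference down, and the sample size has little room for that.

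People who only reviewed the package raise a different issue. Section 5.6.2 presents the AC calls as monitoring of symptoms and lifestyle. A reviewer would know in detail what the SM arm receives. Allocation is unblinded (5.3) and the primary outcome, the GUPI, is self-reported, so that knowledge could alter reporting in either arm. Aim 2 could also be tested partly on people whose feedback shaped the package.

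**Working it through.** **1. Can an exposed person pass the screen?** Take an adult with IC/BPS who was one of the eight, is not in psychotherapy and meets no other exclusion. Prior receipt triggers no item in 4.4 or Appendices A to D. The same holds for a package reviewer. Both can be randomised.

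**2. Do the recruitment routes reach them?** For the eight, the treating clinic is a named source. For focus-group members, the recruitment tools are reused. Re-contact through former studies is plausible: section 5.6.1 identifies the focus groups by IRB #170653, and the PISES entry in 5.7.1 calls #170653 a former investigation. The redaction in 4.1 prevents confirmation.

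**3. Reproduce the plan's sample size.** Inputs from section 9.1: "Assuming a Type I error of 0.05 and power of .90"; GUPI total "normally distributed with a standard deviation of 8.61"; "A 7-point decrease in total GUPI score is considered clinically meaningful"; allocation 2:1. Assumptions: the 7 points are the between-arm difference, and the test is two-sided (neither is stated).

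- Normal approximation: AC n = (1 + 1/2) × (1.960 + 1.282)² × 8.61² / 7² ≈ 23.8, so 24 AC + 48 SM.
- Standard error at 25 and 50: 8.61 × √(1/25 + 1/50) = 2.109. Noncentrality: 7 / 2.109 = 3.32.
- Power from the noncentral t with 73 degrees of freedom: 0.906. At 24 + 48 it is 0.894, so 25 + 50 is the smallest 2:1 pair reaching 0.90. The plan's figure reproduces.

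**4. Allow for exposed completers.** Let m of the 75 completers be exposed, f = m/75, balanced between arms by randomisation. Let e be the SM-AC difference among them. Then

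difference = 7 × (1 − f) + e × f.

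Example: m = 8, e = 0 gives 7 × (1 − 8/75) = 6.25, a loss of 0.75 points.

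| Exposed completers | f | e | Difference | Power (t) |
|---|---|---|---|---|
| 0 | 0 | – | 7.00 | 0.906 |
| 4 | 5.3% | 3.5 (half gain) | 6.81 | 0.890 |
| 4 | 5.3% | 0 (no further gain) | 6.63 | 0.873 |
| 8 | 10.7% | 3.5 | 6.63 | 0.873 |
| 8 | 10.7% | 0 | 6.25 | 0.833 |

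In the last row, restoring 90% power would take 30 + 60 = 90 completers (normal approximation). Power falls below 0.80 at f of about 14.5%, or about 11 of 75, which is more than the eight counted patients. The values of m and e are assumptions; the documents give neither. The contribution of package reviewers cannot be computed without the focus-group size.

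**The case against.** The strongest reply is that this is a possibility with a small likely effect. Nothing says that an exposed person was or will be enrolled. The clinic alone sees about 10 new patients a month, and recruitment spans several clinics, registries, community sources and social media over three years. Having all eight among 75 completers is remote, and Aim 2 is described as seeking pilot data. This stands, and it limits the size of the point.

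Several stronger readings are tempting, but the documents do not support them:

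- *That the eight received the trial programme.* They received a preliminary tailored intervention; the trial protocol was developed after focus groups (5.6.1). Overlap is likely, identity is not shown.
- *That reviewers count as treated.* Reviewing a package for acceptability is not eight 50-minute sessions.
- *That dilution is certain and comes from both arms.* Benefit gained before baseline is already in baseline GUPI, for which the model adjusts, and exposure balances between arms in expectation. An exposed AC patient does not improve during the trial merely because of earlier treatment. Dilution requires that exposed SM patients gain less than others. Neither adjustment nor balance restores that lost increment, so this narrower mechanism survives.
- *That contamination occurs.* No leakage between arms during the trial is shown.

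Knowledge of the arms is also not peculiar to reviewers: Appendices B and C describe both kinds of visit to every candidate. Reviewers know more of the content, but any reporting bias could enlarge the difference as easily as shrink it.

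**Conclusion.** The point holds as a gap in eligibility screening. As written, the plan allows randomisation of people who have had a version of the intervention or reviewed its package, recruits where they can be found, and neither records nor analyses that exposure. The consequence is possible dilution through a smaller SM gain, plus a reporting effect of unknown direction in reviewers.

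The number affected is unknown and probably small. Against a planned power of 0.906, plausible scenarios give about 0.87, and 0.83 only if all eight known patients complete with no further gain. These figures assume a two-sided t-test, a 7-point between-arm difference, SD 8.61, exactly 50 and 25 completers, and the chosen values of e; covariate adjustment and the interim look are ignored. This is a cheap improvement worth making. It does not show that the trial's contrast is compromised.

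**What to change.** Add to section 4.4, and carry through Appendices A to D, an exclusion for prior receipt of the IC/BPS self-management intervention in any version, including the eight-patient preliminary one. Add one screening question to match, and remove known recipients from contact lists before outreach.

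For people who only reviewed the Aim 1 package, exclusion is not needed: ask, record the answer, and add to section 9.1 a sensitivity analysis of the primary outcome without them. Treat anyone exposed who is already enrolled in the same way; section 4.1 refers to enrolment in a first year, so there may be some.

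The cost is one criterion, one question, one recorded variable and one extra analysis, with the loss of a few willing patients. If 75 unexposed completers are still reached, the planned 50 + 25 and power of 0.906 are unchanged.
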